#### 13.12.4. Per Protocol Population (PP)

A sensitivity analysis will be performed for a per protocol (PP) data set as an exploratory approach. The PP population includes all patients who are eligible for FAS evaluation and who additionally do not show major protocol deviations. As noted in section 13.9, the supportive analysis by means of the per-protocol set will be regarded as of equal scientific importance as the FAS analysis, since it most closely reflects the scientific model underlying the protocol (see ICH E9, section 5.2.2).

#### 13.13. Homogeneity Analyses (Exploratory Interpretation)

Homogeneity analyses for baseline shall be performed based on the FAS population.

In addition to descriptive analyses robust nonparametric Mann-Whitney effects size measures and their two-sided 95% confidence intervals shall present an overview on demographic-anamnestic variables and on the primary efficacy criteria at baseline. This allows comparison of baseline variables across different scales and data types.

As benchmark for relevant baseline differences, a Mann-Whitney effects size measure of 0.36 and 0.64 respectively will be applied (referring to a standardized difference of 0.5 according to Cohen, which is regarded as a medium-sized difference).

In the case of heterogeneities, stratified analyses will be performed as second line analyses.

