#### 4.1.1. **Primary Variables**

The following psychometric tests are combined by multivariate analysis with their score changes from baseline at 180 and 360 days after baseline (7 and 13 months after the onset of ischeamic stroke):

- Stroop Color Word test (Stroop)
- Trail-Making-Test Part A (TMT-A)
- Digit Span Backwards Task (DS-BW)
- Digit Symbol (DS-WPSI)

- Verbal Fluency Test CFL Version (VFT-CFL)
- Rey Auditory Verbal Learning Test (RAVLT)

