#### 13.7. Multiplicity

Multiplicity regarding multiple primary outcome measures is controlled by the chosen correlation-sensitive, multivariate test procedure (Wei-Lachin procedure, see also section 13.9).

Mutiplicity regarding the two primary points in time is controlled by means of the principle of *a priori* ordered hypotheses (fixed sequence approach). The procedure of *a priori* ordered hypothesis is most powerful with full control of alpha (for control of alpha using stepwise testing see Maurer W, Hothorn LA, Lehmacher W 1995). The sequence and nature of the a priori ordered test-statistical hypotheses of the trial is defined as follows:

- 1. Combined cognitive outcome measures as defined in section 13.3.2, score changes from baseline to day 180 (month 4 post stroke), multivariate analysis, generalized Wilcoxon-Mann-Whitney test (Wei-Lachin procedure)
- 2. Combined cognitive outcome measures as defined in section 13.3.2, score changes from baseline to day 360 (month 13 post stroke), multivariate analysis, generalized Wilcoxon-Mann-Whitney test (Wei-Lachin procedure)

The principle of *a priori* ordered hypotheses is embedded in the well-known general principle of closed testing. The pre-planned chain of hypotheses can be tested in a confirmatory way with the same full alpha value; each test result smaller than alpha will be statistically significant as long as the preceding test result was also significant.

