#### 13.8. Sample Size Calculation

The power for this study is determined based on the following design specifications:

- Two-sided type I error defined as alpha = 0.05, two-sided (multiple level alpha, see section 13.6)
- Type II error defined as  $\beta = 0.1$  (Testpower 90%)
- Design alternative effect size: Mann-Whitney statistic (MW) = 0.60 (small to medium-sized difference according to Cohen (Colditz, 1988); assuming a normal distribution the effect size MW may easily be re-expressed as the well-known Cohen effect size (Cohen, 1988) of a standardized difference (Cohen's d): MW = 0.60 means Cohen's d = 0.35)
- Estimated correlations among the single outcome scales included in the global statistics  $\rho = 0.6$ )

Nonparametric sample size calculations within the framework of a multiple outcome approach (Wei-Lachin procedure- Wei and Lachin, 1984; Lachin 1992) was performed applying the validated software Nnpar 1.0 from idv Data Analysis and Study Planning, Krailling/Munich (see also Tang, 1999; Lachin, 1981). A good example for sample size calculation according to the Lachin approach (Wei and Lachin, 1984; Lachin 1992; Lachin, 1981) in multidimensional trials with neuroprotective agents is also given by Huang (2008).

Please note: further details of the effect size (Mann-Whitney statistic) are described in section 13.9, further details of sample size assessment are described in the separate document "Sample Size Assessment Based on a Multidimensional Efficacy Approach".

Based on the above design specifications, the total required sample size for the multivariate ensemble results in 145 patients per group (including 15% enhancement for usual "ambiguities", e.g., dropouts). With this sample size a "small to medium-sized" group difference (MW = 0.60) with regard to the multivariate cognitive outcome ensemble can be detected with a power of 90%.

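### The primary test uses baseline only by subtraction: adjusting for it would be a cheap gain in precision, and the MW 0.36/0.64 imbalance benchmark practically never fires

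*Protocol*

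**What the plan says.** Protocol 4.1.1 defines the primary variable: "The following psychometric tests are combined by multivariate analysis with their score changes from baseline at 180 and 360 days after baseline". Section 13.7 fixes the two ordered hypotheses in the same terms, first "score changes from baseline to day 180 (month 4 post stroke), multivariate analysis, generalized Wilcoxon-Mann-Whitney test" and then "score changes from baseline to day 360 (month 13 post stroke), multivariate analysis, generalized Wilcoxon-Mann-Whitney test". Section 13.9 describes the directional Wei-Lachin test without a covariate or stratum. Section 6.7.1 specifies permuted blocks and names no stratification factor. All six scales are measured at Visit 2 (section 11.1).

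Section 13.8 powers the trial on "Design alternative effect size: Mann-Whitney statistic (MW) = 0.60", equated there with Cohen's d = 0.35.

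On baseline comparability, section 13.13 states "As benchmark for relevant baseline differences, a Mann-Whitney effects size measure of 0.36 and 0.64 respectively will be applied", glossed as "referring to a standardized difference of 0.5 according to Cohen, which is regarded as a medium-sized difference". The consequence is: "In the case of heterogeneities, stratified analyses will be performed as second line analyses". The same section reports baseline MW values with 95% confidence intervals for the primary criteria. Sections 4.2.1 and 13.5 list both scores and score changes of each primary scale as secondary variables, and section 13.10 adds MW effect sizes with confidence intervals for them.

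**The concern.** Subtracting baseline is the same as adjusting for it with a slope fixed at 1. When baseline and follow-up correlate at r below 1 and have equal variances, the right slope is r. The change score then over-corrects, and an arm that starts better by chance is marked down through regression to the mean. There are two costs: extra variance in every trial, and a shift in the particular trial that happens to be imbalanced.

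The plan's stated response to imbalance does not help. Its threshold is larger than the effect the trial is looking for, and even when crossed it leaves the primary test as it is. The fixed sequence adds weight to the precision cost, because a miss at day 180 closes the route to a confirmatory claim at day 360.

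**Working it through.** **Inputs from the protocol.** MW 0.60 (d = 0.35), two-sided alpha 0.05, power 90%, correlation among scales 0.6, 145 per group including 15% (13.8); six scales (13.3.2); benchmark 0.36/0.64 (13.13). **Assumption:** r is not given, so 0.5 to 0.8 is used.

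**1. The plan's own sample size.** For the directional Wei-Lachin test the single-scale n is multiplied by (1 + 5 × 0.6)/6 = 4/6. With d = 0.35:

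n = 2 × ((1.96 + 1.2816)/0.35)² × (π/3) × 4/6 = 120, and 120/0.85 = 142.

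This is within 3% of 145. With MW exactly 0.60, Noether's formula gives 117, then 138. At 145 × 0.85 = 123 evaluable per group, power is 91.4%. The 90% statement holds up.

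**2. Benchmark against target.** d = √2 × Φ⁻¹(MW), so 0.64 is d = 0.51 and 0.60 is d = 0.36. The benchmark is about 1.4 times the effect sought.

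**3. How often the benchmark is reached under randomisation.** SE of a baseline MW = √((2n + 1)/(12n²)).

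| n per group | SE | 0.14/SE | chance, one scale | upper bound, any of six | 95% chance range |
|---|---|---|---|---|---|
| 145 | 0.034 | 4.1 | 0.004% | 0.02% | 0.43 to 0.57 |
| 123 | 0.037 | 3.8 | 0.015% | 0.09% | 0.43 to 0.57 |

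**4. Shift caused by a plausible imbalance.** A 1.96-SE imbalance on one scale at n = 145 is MW 0.567, or d = 0.24. The change score carries (1 − r) × d, and its SD is √(2(1 − r)), so:

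shift in MW = Φ(d × √(1 − r)/2) − 0.5 = 0.033 (r = 0.5), 0.026 (r = 0.7), 0.021 (r = 0.8).

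The planned shift is 0.60 − 0.50 = 0.10.

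**5. Precision.** Variance ratio, adjusted to change, is (1 + r)/2. If the change-score test has 90% power, the adjusted power is Φ(3.2416/√((1 + r)/2) − 1.96).

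| r | variance ratio | adjusted power | adjusted n matching 145 |
|---|---|---|---|
| 0.5 | 0.75 | 96.3% | 109 |
| 0.7 | 0.85 | 94.0% | 124 |
| 0.8 | 0.90 | 92.7% | 131 |

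**6. Simulation** (six scales, correlation 0.6, 123 per group, MW 0.60 on change). Power rose from 93% to 97–98% at r = 0.5, from 92–93% to 94–95% at r = 0.7, and from 93% to 95% at r = 0.8. Type I error stayed near 5%. At r = 0.5, change-score power was 99% in the tenth of trials with the lowest test-arm baseline and 73% in the tenth with the highest. Adjusted power was 98% and 97%.

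**7. Worst ranks.** If worst ranks are assigned before residuals are taken, they need not stay worst. With an assumed 5% code 2, r = 0.6 and 246 patients, about 59% of code 2 patients ended with a better residual than at least one survivor. Assigning the worst rank after residualising kept the gain: 85% to 91% at r = 0.5 and 83% to 87% at r = 0.7, with type I error 4–5%.

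**The case against.** The change-score test is prespecified and legitimate, and most of the case for it stands.

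- A reader might infer that the primary test is biased or invalid. It is not. Over all randomisations it is unbiased and holds 5%. The shift in step 4 is conditional on the imbalance that occurs, and its variability is already in the test's standard error.
- A reader might infer that the stated 90% power is wrong. Step 1 does not support that, provided MW 0.60 refers to change scores, which section 13.8 does not say. The loss is relative to a better-adjusted analysis.
- A reader might take a baseline MW of 0.60 as the typical hazard, since it would shift the change-score MW by 0.039 to 0.050 (r = 0.7 to 0.5). It is rare: 0.10/0.034 = 2.9 SE, p about 0.003 for one scale. If baselines correlate at 0.6, the six-scale average has SE 0.034 × √(4/6) = 0.028, so it lies 3.6 SE out, p about 0.0003.
- A reader might think the benchmark is the only safeguard, or that the primary test changes when it is crossed. Neither is so. Raw follow-up scores (slope 0) and changes (slope 1) are both reported and bracket a linear adjustment with a slope between 0 and 1. Baseline MWs with intervals would show an imbalance. Leaving the confirmatory test independent of observed imbalance is sound practice.
- Setting the benchmark beside the design effect compares a baseline-score MW with a change-score MW. Their SDs agree only at r = 0.5 with equal variances, so the factor of 1.4 is approximate.

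The unseen SAP may add adjusted sensitivity analyses, but these would not alter the primary test variable fixed in section 13.7.

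**Conclusion.** The point holds as an efficiency improvement, not as a flaw that invalidates the test. For assumed r of 0.5 to 0.8, adjustment is worth about 2 to 6 power points, equivalent to reaching the same power with roughly 109 to 131 per group instead of 145. The gain shrinks towards zero as r approaches 1. It also removes most of a conditional shift of about 0.02 to 0.03 in a scale's MW under a plausible imbalance. The 0.36/0.64 benchmark is about 4 SE out and beyond the design effect, so it is uninformative as a test of relevant imbalance. These sizes rest on the assumed r, equal variances at baseline and follow-up, and roughly normal scores.

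**What to change.** Keep the Wei-Lachin test and change its input. At days 180 and 360, for each scale, prespecify as primary the residuals of follow-up ranks regressed on baseline ranks, arms pooled, fitted in patients with valid or LPCF-imputed values. Then assign deaths and code 2 the worst rank, after residualising, so that they stay below all others. Keep unadjusted change scores as the sensitivity analysis. In section 13.13 keep the descriptive baseline MWs and intervals, but do not use 0.36/0.64 to decide whether adjusted or stratified analyses are done.

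The cost is an amendment with matching SAP text, settled before unblinding, and slightly more programming. No new data are needed, because the baselines are already collected. The downside is a less direct patient-level reading of the MW and one added linear step in a plan that aims to minimise assumptions. The unadjusted sensitivity analysis still gives the direct reading.

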#### 13.14. Compliance

Patients with compliance for the entire study below 80% for the treatments will be considered protocol violators and will not be included in the per protocol analysis.

#### 13.15. Blind Review and Final Statistical Analysis Plan

A blind review of the data shall be performed within the framework of the requirements of the ICH Guideline E9. The statistical analysis plan will be finalized by the statistician before the decoding takes place. The analysis populations (Safety, FAS, and PP) will be listed individually in the final statistical analysis plan.

Formal records will be kept of when the statistical analysis plan was finalised as well as when the blind was subsequently broken.

#### 13.16. Software Applied

Nonparametric sample size calculation was performed applying the validated software Nnpar 1.0 from idv Data Analysis and Study Planning, Gauting/Munich.

The data analysis will be performed in a validated working environment according to the requirements of the ICH-Guidelines E3 (1995). The software to be used for data evaluation will be described in the final statistical analysis plan.

#### 14. ACCESS TO SOURCE DATA / DOCUMENTS

The Investigator will permit study-related monitoring, audits, IRB / IEC review and regulatory inspections, providing direct access to primary patient data (i.e. source data) which supports the data on the CRFs for the study, i.e. general practice charts, appointment books, original laboratory records etc.

#### 14.1. Source Data

Source data are defined as all information in original records and certified copies of original records of clinical findings, observations or other activities in a clinical study necessary for the reconstruction and evaluation of the study. Source data are contained in source documents (original records or certified copies).

#### 14.2. Source Documents

Source documents are defined as original documents, data and records (e.g. hospital records, clinical and office charts, laboratory notes, memoranda, patient diaries or evaluation check lists, pharmacy dispensing records, recorded data from automated instruments, copies or manuscripts certified after verification as being accurate copies, microfiches, photographic negatives, microfilm or magnetic media, patient files, records kept at pharmacy, at the laboratories and at medico technical departments involved in clinical study).

#### 14.3. Direct Access

Direct access is defined as the permission to examine, analyse, verify and reproduce any records and reports that are important to evaluation of a clinical study. Any party (e.g. domestic and foreign regulatory authorities, the Coordinator and / or authorised representatives of the Coordinator such as monitors and auditors) with direct access should take all reasonable precautions within the constraints of the applicable regulatory requirements to maintain the confidentiality of patient identities and Coordinator proprietary information.

#### 15. QUALITY CONTROL AND QUALITY ASSURANCE

#### 15.1. Quality Control

Quality Control is defined as the operational techniques and activities, such as monitoring, undertaken within the quality assurance system to verify that the requirements for quality of the study related activities have been fulfilled.

Quality Control should be applied to each stage of data handling to ensure that all data are reliable and have been processed correctly.

#### 15.2. Study Monitoring

Authorized, qualified Clinical Trial Monitor will visit the investigational site in regular intervals, established based on the needs of the project, to verify adherence to protocol and local legal requirements, to perform source data verification and to assist the Investigator in his study related activities.

#### 15.3. Quality Assurance

Quality Assurance is defined as the planned and systematic actions that are established to ensure that the study is performed and the data are generated, documented (recorded) and reported in compliance with Good Clinical Practice (GCP) and the applicable regulatory requirements.

#### 15.4. Inspection

An Inspection is defined as the act by an authority (IRB/IEC) of conducting an official review of documents, facilities, records and any other resources that are deemed by the authorities to be related to the clinical study and that may be located at the site of the study, or at the Coordinators and / or clinical research organisation facilities or at any other establishments deemed appropriate by the authorities.

#### 15.5. Audit

An audit is a systematic and independent review of study related activities and documents to determine whether the validated study related activities were conducted and the data were recorded, analysed and accurately reported according to the protocol, designated Standard Operating Procedure (SOPs), Good Clinical Practice (GCP) and the applicable regulatory requirements. An independent audit at the study site may take place at any time during or after the study.

#### 15.6. 13.5 Risk-Based Centralized Statistical Monitoring

In accordance to the most recent requirements of the ICH E6 Guideline for Good Clinical Practice (GCP, Amendment R2, July 2015), the EMA reflection-paper on Risk-based Quality Management in Clinical Trials (2013), and the FDA Guidance for Industry on a Risk-based Approach to Monitoring (2013), a risk-based centralized statistical approach to monitoring is introduced in combination with targeted on-site monitoring for ongoing surveillance of study conduct, thus ensuring highest standards of data quality and integrity.

#### 16. ETHICAL AND LEGAL CONSIDERATIONS

#### 16.1. Ethical Considerations

Before initiating a study, the Investigator will have written and dated approval / favourable opinion from the relevant IRB / IEC for the study protocol as well as for any amendments. Approval will be indicated in writing with reference to the final protocol number and date. Details of the IRB / IEC's constitution including names of its members and their function in the committee (e.g. chairman, specialist, lay-member) should be made available for inclusion in the Trial Master File.During the study all documents that are subject to review should be provided to the IRB / IEC by the Investigator.

#### 16.2. Independent Ethics Committee (IEC) / Institutional Review Board (IRB)

The study protocol including all amendments and the study CRF will be submitted to the IRB/EC of the study centre before initiation of the study. IRB/EC approval for the study protocol and all amendments will be obtained prior to the start of any study specific procedures.

#### 16.3. Informed Consent

Patients will be informed about the study procedures and potential risks and benefits of the study. Their consent to participate in this study will be obtained before any study-specific procedures are carried out. A sample informed consent is provided in Appendix 2.

#### 16.4. Modification of Protocol

The Investigator or the Coordinator should not implement any deviation from, or changes of, the protocol without mutual agreement, prior review and documented approval from the IEC of a respective amendment. The only exceptions are where necessary to eliminate an immediate hazard to study patients, or when the changes involve only logistical or administrative aspects of the study (e.g. change in monitor(s), change of telephone number(s)).

The party initiating an amendment must confirm it clearly in writing and it must be signed and dated by the Coordinator and the Coordinating Investigator. Necessary protocol amendments will be submitted to the appropriate IECs and can only be implemented after a favourable opinion from the IEC has been obtained and is documented in writing.

#### 16.5. Conduct of Study

This clinical study will be conducted in accordance with the Declaration of Helsinki. It will be conducted in compliance with this protocol, Good Clinical Practice (2001/20/ EEC,

CPMP/ICH/135/95), designated Standard Operating Procedures, and with local laws and regulations relevant to the use of investigational new drugs in the country of conduct.

#### 16.6. Personal Data and Data Protection

All data obtained in the context of the clinical study are subject to data protection. The patient's name in addition to other data related to persons (excluding date of birth / age and sex) are not to be disclosed by the Investigator or the investigating physicians. The latter shall take care that the case report forms or other documents (e.g. copies of reports on special findings) transmitted to the FSNN contain no names, but another identifier. The storage of data for statistical assessment shall be performed under the patient's identifier. Only the Investigator and the investigating physicians can perform assignment of the identifier to the personal data.

If it becomes necessary in the course of the study to identify a patient's name for medical reasons, all the individuals involved are subject to an obligation to maintain secrecy.

If personal data are stored and processed, the requirements of data protection legislation are to be observed.

#### 16.7. Data Handling and Record Keeping

#### 16.7.1. Completion of Case Report Forms

Any data to be recorded directly into the CRFs will be identified at the start of the study.

The investigator must ensure the accuracy, completeness legibility and timeliness of data reported in the CRF and all required reports. Any change or correction to a paper CRF must be dated, initialled and explained (in case of an eCRF data entries are already monitored by an audit trail) and must not obscure the original entry, this applies to both written and electronic changes.

Data reported on the CRF that are derived from source documents must be consistent with the source documents or the discrepancies should be explained.

Within two weeks after completion of each patient, the Investigator should agree to have completed and signed CRFs available for full inspection by the clinical monitor.

#### 16.7.2. Archiving

On termination of the study, the study documents, including the emergency envelopes are to be returned to the Coordinator. These records are to be retained for the periods required by ICH-GCP, i. e. until at least 2 years after the last approval of a marketing application in an ICH region and until there are no pending or contemplated marketing applications in an ICH region or at least 2 years have elapsed since the formal discontinuation of clinical development of the Investigational Product (CPMP/ICH/135/95), or by national legal

requirements, whichever is longer, but not less than 15 years after routine/premature termination of a clinical study.

The final report shall be retained for at least 2 years after the Investigational Products are removed from the last market. The informed consent forms and all the original (raw) data are to be retained by the head of the clinical study or the investigating physicians for at least 15 years.

